### 2.5.3 Handling of missing values/censoring/discontinuations

For every patient, it can be determined whether he/she discontinued for AE-related reasons. AE-related discontinuations are counted as events. Discontinuation due to the other reasons as non-AE-related treatment discontinuations or losses to follow up should not be counted as event.

[REDACTED]

[REDACTED]

- | [REDACTED]
- | [REDACTED]
- | [REDACTED]

[REDACTED]

[REDACTED]

[REDACTED]

[REDACTED]

[REDACTED]

[REDACTED]

[REDACTED]

[REDACTED]

[REDACTED]

[REDACTED]

## **2.6 Analysis of the secondary objective**

The secondary objective of the study is to evaluate the effect of erenumab compared to the topiramate on the proportion of patients with at least 50% reduction from baseline in monthly migraine days.

Analysis on primary endpoint should be done based on the Full Analysis Set (FAS).

### **2.6.1 Secondary endpoint**

The secondary endpoint is an achievement of at least 50% reduction from baseline in MMD over the last 3 months (month 4, 5, and 6) of the double-blind epoch.

The secondary analysis will contrast erenumab versus topiramate in the FAS.

## 2.6.2 Statistical hypothesis, model, and method of analysis

Null hypothesis: odds of achievement of at least 50% reduction from baseline in MMD are equal in both treatment groups.

Alternative hypothesis: odds are not equal when comparing erenumab to topiramate

Statistical hypothesis:  $H_0$ :

$$(p_1 / (1 - p_1)) / (p_0 / (1 - p_0)) = 1,$$

where

$p_j$  – probability of patients achieved at least 50% reduction from baseline in the treatment group  $j$

$j = 0$  corresponds to topiramate group

$j = 1$  corresponds to erenumab group

The odds ratio not significantly different from one would mean that there is no evidence for a difference in achieving at least 50% reduction from baseline between the two treatment groups.

Statistical hypothesis will be tested in the frame of logistic regression analysis controlling for the stratification factor:

$$\text{logit}(\text{probability}) = \text{treatment group} + \text{stratification factor}$$

Odds ratio, its 95% confidence interval and the corresponding p-value will be presented. Significance level will be set at 5%. By significant test results ( $p(\text{odds ratio} = 1) \leq 0.05$ ) the superiority of erenumab will be claimed only by the correct direction, i.e. if the erenumab odds are higher than topiramate odds.

Additional to the odds ratios, estimates for the relative risk and the risk difference (with 95% confidence intervals and p-values) will be calculated for the secondary endpoint. Confidence intervals and p-values for the relative risks and risk difference should be calculated based on the normal distribution.

In case of zero events in only one treatment arm add 1 patient with 0.5 events to each treatment arm for calculation of the relative risk. Odds ratio will not be estimated in this case.

In case of zero events in both treatment arms no odds ratio will be estimated, the null hypothesis will not be tested and no difference between treatment arms can be claimed. Additionally, no relative risk will be calculated.

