9.4 Analysis of secondary variables

The secondary variable is the achievement of at least a 50% reduction from baseline in monthly migraine days (MMD) over the last 3 months (months 4, 5, and 6) of the double-blind treatment period.

The analysis of the primary variable will be based on the following estimand:

- Population – Full Analysis Set (FAS)
- Variable of Interest: number of patients with at least 50% reduction from baseline in monthly migraine days (MMD)
- Intercurrent event: discontinuation of study medication – effect between erenumab versus topiramate assuming to evaluate treatment policy
- Intercurrent event: discontinuation of study or lost to follow up – effect between erenumab versus topiramate assuming no response could be achieved
- Summary measure – odds ratio

All the subjects’ data collected regarding 50% response of MMD will be used in the analysis regardless whether subjects complete the study drug or not. Subjects with missing response information on this endpoint will be imputed as non-response (non-responder imputation). A logistic regression model including treatment group, baseline value, and stratification factor will be used to perform the treatment comparison (erenumab vs. topiramate) at end of the DBTE. Additional to the odds ratio obtained from the logistic regression, estimates for the risk ratio and the risk difference (with corresponding confidence intervals and p-values) will be calculated for the secondary endpoint.

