## 1 Introduction

The purpose of this statistical analysis plan (SAP) is to provide details of the statistical analysis according to Section 9 of the study protocol v02 for AMG 334 Study CAMG334ADE01 dated June 6, 2019. The scope of this plan includes the primary, secondary, and exploratory analyses, which will be executed by the CRO (██████████).

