End of trial will occur when the last patient completes last visit (LPLV).

Figure 1-1 Study Design

Patients will be stratified into groups according to their number of migraine days during the baseline epoch (4 - 7 vs. 8 - 14 vs.  $\geq 15$  monthly migraine days).

[figure not shown]
The study will recruit approximately 375 patients per arm (750 total) including up to a maximum of 35 patients with  $\geq 15$  monthly migraine days per arm (approx. 10 % of patients per arm). Assumptions were based on clinical studies with topiramate and erenumab.

No interim analysis is planned.

[figure not shown]

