#### **Stratification factor (for randomization)**

Monthly Migraine Days (MMD) category (4 - 7, 8 - 14,  $\geq$  15 MMD) at baseline as used for randomization of patients.

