**5.1.2.2 Other imputations**

**5.1.2.2.1 eDiary data**

Missing eDiary data in the calculation of monthly measurements about patients' migraine and non-migraine headaches will be handled using the following method:

1. For **monthly intervals with  $\geq 14$  days of eDiary days** (including retrospective eDiary days) in each interval:

Monthly migraine days will be prorated to 28-day equivalents. Prorated result does not need to be rounded.

2. For **monthly intervals with  $< 14$  days of eDiary use** (including retrospective eDiary days), all monthly measurement will be set to missing.

Monthly Endpoint	Condition	Proration Method (does not need to be rounded)
Monthly migraine days	
If eDiary days in entire baseline or interval post baseline <math>\geq 14</math> (including retrospective eDiary days), then do proration;
 
Else monthly measurement is set to missing
 
[eDiary day is a day with all headache related questions completed retrospectively or not]
	
Number of observed migraine days * 28/ Number of information days in interval
 
[information day is an eDiary day or headache day]

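### SAP 2.6.2 drops the baseline value that protocol 9.4 puts in the secondary-endpoint model; the effect is usually small, but one model should be named before unblinding

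*SAP*

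**What the plan says.** Protocol 9.4, on the 50% responder endpoint: "A logistic regression model including treatment group, baseline value, and stratification factor will be used to perform the treatment comparison". That is three terms. Protocol 9.3.2 gives the primary endpoint only treatment and stratification factor, so the protocol itself sets the two models apart.

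SAP 2.6.2, on the same endpoint: "Statistical hypothesis will be tested in the frame of logistic regression analysis controlling for the stratification factor". The equation that follows has treatment group and stratification factor only. The same section sets a 5% significance level and adds that "the superiority of erenumab will be claimed only by the correct direction", meaning higher odds of response on erenumab. Protocol 9.4 states neither a significance level nor a superiority rule for this endpoint.

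Three other parts of the SAP bear on the point:

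- Its introduction gives its purpose as "to provide details of the statistical analysis according to Section 9 of the study protocol v02".
- SAP 2.1.1 defines the stratification factor as the MMD category (4-7, 8-14, 15 or more) "at baseline as used for randomization of patients".
- SAP 5.4.2 refers back to the secondary-objective section, so no visible text restores the missing term.

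**The concern.** The two current documents name different models for one treatment comparison, and no visible text says which prevails. The superiority rule is tied to the model that departs from the protocol, although the SAP presents itself as detailing the protocol's analysis section.

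Both models are valid tests, so this is a matter of pre-specification rather than bias. If the secondary result falls close to p = 0.05, the models could give opposite verdicts, and a reader with both documents could ask whether the choice followed the result. The two odds ratios also condition on different covariates. That matters because the protocol intends the data to support health technology assessments, where the estimate is read as well as its p-value.

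**Working it through.** **Step 1: the terms side by side.**

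| Term | Protocol 9.4 | SAP 2.6.2 |
|---|---|---|
| Treatment group | yes | yes |
| Stratification factor | yes | yes |
| Baseline value | yes | no |
| 5% level and superiority rule | not stated | stated |

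Missing responses count as non-response in both documents. The only model difference is the baseline value, naturally read as baseline MMD.

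**Step 2: inputs.** From the documents: 1:1 allocation (protocol 5.2), the three strata, and "approximately 375 patients per arm (750 total) including up to a maximum of 35 patients with" at least 15 MMD per arm (SAP 1.1). The top stratum is therefore at most 35/375 = 9.3%. The documents give no topiramate responder rate, no relation between baseline and response, and no power figure for this endpoint, so there is no stated figure to reproduce.

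Assumed:

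- stratum shares of 36%, 54.7% and 9.3%;
- baseline uniform within strata, on 4-7.99, 8-14.99 and 15-24 days;
- a 30% topiramate response;
- a slope of 0, -0.05, -0.10 or -0.20 logits per baseline day.

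**Step 3: how much of baseline the strata already carry.** Under these assumptions the within-stratum variance (width²/12, weighted) is 0.36×1.327 + 0.547×4.072 + 0.093×6.75 = 3.33. The stratum means are 5.995, 11.495 and 19.5, with an overall mean of 10.26. The between-stratum variance is 0.36×4.264² + 0.547×1.236² + 0.093×9.241² = 15.32. The share left to the continuous covariate is 3.33/(3.33 + 15.32) = 18%.

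**Step 4: anchor for power.** For 30% vs 40% at 375 per arm, the standard error is √((0.21 + 0.24)/375) = 0.0346, or 0.0348 pooled. Power is Φ((0.10 − 1.96×0.0348)/0.0346) = 82.0%.

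**Step 5: both models fitted to the same simulated trials** (2,000 per setting, Wald test, two-sided 5%). The treatment effect is the conditional odds ratio implied by each pair of rates: 1.56 for 30% vs 40%, and 1.40 for 30% vs 37.5%.

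| Rates | Slope | Power, SAP model | Power, protocol model | Verdicts differ |
|---|---|---|---|---|
| 30% vs 40% | 0 | 82.9% | 82.8% | 0.8% |
| | -0.05 | 83.5% | 83.3% | 1.2% |
| | -0.10 | 80.5% | 80.9% | 1.7% |
| | -0.20 | 76.0% | 77.1% | 3.7% |
| 30% vs 37.5% | 0 | 57.6% | 57.6% | 0.9% |
| | -0.05 | 57.8% | 58.0% | 1.6% |
| | -0.10 | 55.8% | 56.6% | 2.6% |
| | -0.20 | 54.6% | 55.5% | 5.9% |

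With no treatment effect, two-sided rejection was 4.8-5.2% for the SAP model and 4.8-5.4% for the protocol model. With 23.5% vs 39.9% (the placebo and erenumab 70 mg rates from the chronic-migraine study in protocol 1.1, used only as an illustration), power exceeded 99% and verdicts differed in at most 0.3%. Average odds ratios from the two models were within about 2% in every setting. At 350 per arm (the protocol summary gives 700 patients), with 30% vs 40% and slope -0.10, power was 77.2% under both models and verdicts differed in 2.0%.

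**Step 6: no assumed slope.** A second simulation drew migraine-day counts and defined response as follow-up at or below half of the patient's own baseline, so regression to the mean arises by itself. Response rates were about 30% vs 30%, 37.5% and 42%. Verdicts differed in 0%, 1.3% and 0.4% of trials, and the odds ratio moved by at most 0.002.

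**Step 7: near the threshold.** A further set used 4,000 trials per setting, N = 750, 70 patients in the top stratum, other baselines about N(9, 3.5) restricted to 4-14 days, 30% topiramate response and a conditional odds ratio of 1.5. Among trials whose SAP-model p lay between 0.02 and 0.10, verdicts differed in 3.9%, 5.4%, 7.9% and 17.2% for the four slopes. Over all trials the figures were 0.8%, 1.2%, 1.8% and 4.3%.

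**The case against.** The strongest reply is that this is a tidy-up. The stratification factor already is baseline MMD, so the omission may be deliberate. For HIT-6 and SF-36, where baseline is a different measurement from the stratifier, SAP 2.7.2 does list the baseline value with the stratification factor. Type I error, power and odds ratio barely move. The 17.2% figure needs the steepest slope and a band where any small model change flips verdicts, and no slope is supported by the documents. The SAP on its own is unambiguous about the model that carries its rule. SAP sections 3 and 4 and most of the change list for protocol amendment 2 are redacted, so a declared change may sit there.

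Most of this stands as a limit on size. The slope-free simulation supports the low end of the range, and nothing can be concluded from the absence of a visible explanation. It does not remove the conflict: protocol 9.4 and SAP 2.6.2 are both current and differ in a model term. That the omission could be reasoned is an argument for writing the reason down.

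**Conclusion.** The concern holds. The SAP's decision rule for the sole secondary endpoint sits on a model that lacks a covariate the protocol specifies. That rests on the text alone and needs no simulation.

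The consequence is modest: both tests are valid, and the two models gave different superiority verdicts in roughly 0 to 3% of trials for slopes up to -0.10 per day and in up to about 6% at -0.20 with middling power. These sizes depend on assumed response rates, baseline distributions and slopes. The choice is material only for a result near p = 0.05. The discrepancy should be corrected, but it does not threaten the analysis.

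**What to change.** Before unblinding, write the SAP 2.6.2 model as logit(response) = treatment group + baseline MMD + stratification factor. State that this model carries the 5% superiority rule, and report the model without baseline MMD as a sensitivity analysis. If the term was left out on purpose, record that in the SAP as a change from protocol 9.4 with its reason, and report the protocol model as the sensitivity analysis.

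The covariate is already derived: under the eDiary rules in SAP 5.1.2.2.1, "Monthly migraine days will be prorated to 28-day equivalents. Prorated result does not need to be rounded", and this covers the baseline interval. The cost is SAP wording and one model term, with no new data, patients or visits.

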## 2.6.3 Handling of missing values/censoring/discontinuations

All the subjects' data collected regarding 50% response in MMD will be used in the analysis regardless of whether subjects discontinue study treatment or not. Subjects with missing response information on this endpoint will be imputed as non-response (non-responder imputation).

## 2.6.4 Subgroup analyses

Not applicable.

## 2.7 Analysis of exploratory objectives

### 2.7.1 Exploratory endpoints

Exploratory efficacy analyses of erenumab in comparison to topiramate is based on patients' reported data assessed via eDiary, including

- [REDACTED]
- Patients' quality of life assessed with SF-36v2 (The Short Form (36) Health Survey)
- Headache impact on patients' functional ability assessed by HIT-6 (Headache Impact Test)

■ [REDACTED]

Objectives of the exploratory efficacy analyses are listed in the table below.

Exploratory objective	Efficacy endpoint	Assessment time point
[REDACTED]	[REDACTED]	[REDACTED]
To evaluate the effect of erenumab compared to topiramate on functional impairment	[REDACTED]	Week 24
[REDACTED]	HIT-6: Proportion of patients achieving at least a 5 points reduction from baseline	Week 24
To evaluate the effect of erenumab compared to topiramate on generic health-related quality of life	[REDACTED]	Week 24
	SF-36 v.2: Proportion of patients achieving at least a 5 points increase from baseline in PCS- and MCS score	Week 24

[figure not shown]
**2.7.2 Statistical hypothesis, model, and method of analysis**

Analysis of exploratory efficacy endpoints will utilize the FAS. Subjects will be analyzed according to their randomized treatment group.

Methods of analysis for exploratory efficacy analyses are summarized in the table below.

Exploratory Endpoint	Model	Terms included in the model	Imputation of missing values	Additional

		scheduled visit)		Treatment difference will be tested using a contrast from the model
Proportion of patients achieving at least a 5 points reduction from baseline in HIT-6 total score	Logistic regression model	
 
- treatment group
 
- baseline value
 
- stratification factor
 
	Non-response imputation	Summary statistics for observed data  Relative Risk**  Risk Difference**
SF-36 quality of life:  Proportion of patients achieving at least 5 points increase from baseline to week 24 in PCS and MCS	Logistic regression model	
 
- treatment group
 
- baseline value
 
- stratification factor
 
	Non-response imputation	Summary statistics for observed data  Relative Risk**  Risk Difference**

\* MMRM: unstructured covariance matrix will be used in the repeated statement  
\*\*Calculation of the Relative Risk and Risk Difference will be based on rules described for primary analysis, see [Statistical hypothesis, model, and method of analysis](#)

### **2.7.3 Handling of missing values/censoring/discontinuations**

For the exploratory endpoints “Proportion of patients achieving at least a 5 points reduction from baseline in HIT-6 total score” and “Proportion of patients achieving at least 5 points increase from baseline to week 24 in PCS and MCS (SF-36v2)” missing response data will be imputed as non-response (non-responder imputation).

## **2.8 Safety analyses**

Safety analyses will be based on safety data set (SAF).

All safety analyses will be performed for the Double-Blind Treatment Epoch and Follow-up Epoch separately and in descriptive manner.

Missing data will not be imputed for safety endpoints.

### **2.8.1 Adverse events (AEs)**

In the frame of safety analysis the following treatment-emergent AE types will be considered:

- Any AE
- Study treatment related AE
- AE leading to study treatment discontinuation
- AE leading to dose adjustment (including study treatment discontinuation)
- AE leading to pausing in uptitration

- Serious AE (SAE)
- Study treatment related SAE
- SAE leading to study treatment discontinuation
- Death

All adverse events tables will be summarized by treatment group.

The Medical Dictionary for Regulatory Activities (MedDRA) version 22.1 or later will be used to code all adverse events (AE) to a system organ class (SOC) and a preferred term (PT).

Overview table of the number and percentage of patients having each type of AE.

Tables with the *summary types I* will be provided for all AEs listed above except for death. Tables with the *summary types II* will only be provided for AE type ‘any AE’.

*Summary type I:* Tables with number and percentage of patients having particular AE summarized by treatment group, SOC and PT. Summaries will be provided for each AE type separately.

*Summary type II:* Tables with number and percentage of patients having particular AE summarized by treatment group, SOC, PT and severity. Summaries will be provided for each AE type separately.

The SOCs will be presented in the alphabetic order and PTs will be ordered within the SOCs by decreasing order of frequency in the erenumab treatment group.

If a patient reported more than one adverse event with the same PT, the adverse event with the greatest severity will be presented. If a patient reported more than one adverse event within the same primary system organ class, the patient will be counted only once with the greatest severity at the system organ class level, where applicable.

All AEs, deaths (see [Section 2.8.2](#) for details), SAEs and AEs leading to permanent study drug discontinuation will be listed separately.

### **2.8.1.1 Adverse events of special interest / grouping of AEs**

Not applicable.

### **2.8.2 Deaths**

Deaths will be listed by treatment group including the start date of the study treatment, the last date on study treatment, the death date and the reason for death.

### **2.8.3 Laboratory data**

Summary statistics of laboratory hematology- and blood chemistry results will be presented as absolute value as well as change from baseline by visit, treatment and laboratory test category. Change from baseline will be summarized for each time point and only for patients with both baseline and post-baseline assessment.

Clinically notable laboratory values will be flagged and listed by treatment group.

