Patients who are not able to tolerate 50 mg have to be discontinued from drug, but should remain in the trial for documentation purposes. During this time, patients may use treatments described under 5.5.6 for their acute migraine attacks.

Maintenance phase (start of week 7 to end of week 24):

Control-IMP doses are determined during the uptitration phase and must not be changed during the 18-week maintenance phase. Patients have to remain on their highest tolerated dose (50 mg, 75 mg or 100 mg topiramate) throughout maintenance phase. If a patient cannot tolerate dose during maintenance phase, he/she has to be discontinued from all study treatment, but should remain in the trial. This patient is allowed to continue using rescue medication as described under 5.5.6.

All kits of study treatment assigned will be recorded in the IRT. Novartis monitors will reconcile treatment assigned vs treatment administered and ensure that the information is congruent during their monitoring visits.

Tapering off

Control-IMP should be tapered off by patients who complete the study (Visit 199, end of week 24) or discontinue study treatment after receiving a daily dose of 75 mg or 100 mg Control-IMP. Tapering off is performed by reducing the daily dose of Control-IMP by 50 mg for one week before a patient stops taking the drug.

Exemplatory Tapering off scheme:

Patient on 100 mg/day topiramate --> One week 50 mg/day topiramate --> No more medication

Patient on 75 mg/day topiramate --> One week 25 mg/day topiramate --> No more medication

Patient on 50 mg/day topiramate --> No more medication (no tapering off required)

Patient on 25 mg/day topiramate --> No more medication (no tapering off required)

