5.6.2 Discontinuation of study treatment

Discontinuation of study treatment for a patient occurs when study drug is stopped earlier than the protocol planned duration, and can be initiated by either the patient or the investigator.

The investigator must discontinue study treatment for a given patient if, on balance, he/she believes that continuation would negatively impact the risk/benefit of trial participation.

Study treatment must be discontinued under the following circumstances:

- Patient wish
- Pregnancy (see Section 6.5.6 and Section 7.5)
- Use of prohibited treatment as per recommendations in Table 5-1
- Any situation in which study treatment might result in a safety risk to the patient
- Any laboratory abnormalities that in the judgment of the investigator, taking into consideration the patient's overall status, prevents the patient from continuing participation in the study

If discontinuation of study treatment occurs, the patient should NOT be considered withdrawn from the study, and should continue recording in the eDiary as per protocol. Also, patients who discontinued treatment from the double-blind treatment epoch will follow the abbreviated visit schedule until the follow up visit (week 28) is reached (Table 6-2). These visits should be performed with all assessments outlined in Table 6-2. At a minimum, the following data should be collected at clinic visits or via telephone visits:

- new/concomitant treatments
- adverse events / serious adverse events

If the patient cannot or is unwilling to attend any visit(s), the site staff should maintain regular telephone contact with the patient, or with a person pre-designated by the patient. This telephone contact should preferably be done according to the study visit schedule.

Patients who prematurely discontinue the study for any reason should be scheduled for a visit as soon as possible, at which time all of the assessments listed for the final visit (Visit 199) will be performed. At this final visit, the adverse event and concomitant medications should be reconciled on the eCRF. Patients will return for a follow-up visit approximately 8 weeks after their last dose of study medication, and perform the study procedures outlined in Table 6-1.

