- 3 – Including prior prophylactic medication.
- 4 – Includes blood pressure, pulse and temperature.
- 5 – Patient brings to each visit for use at site
- 6 – To be completed during applicable study visits before study drug administration, where applicable.
- 7 – Should also be performed at unscheduled visits.
- 8 – SAEs will be collected after signing of the informed consent through the end of the Follow-Up Epoch (8 weeks after the last IMP injection). Non-serious AEs will be collected after randomization (Visit 101) through the end of the Follow-Up Epoch (8 weeks after the last IMP injection).
- 9 – Study drug is administered by study staff, during the applicable study visits, q.m., s.c..
- 10 – Oral study drug will be dispensed to the patient at the center during the applicable study visit for home application.
- 11 – Sites will access the Interactive Response Technology (IRT) System to register study early termination.
- 12 – Should be additionally performed at any visit if deemed necessary by the investigator due to AEs.
- 13 – Should be performed/registered by the investigator prior to dosing during DBTE.
- TD = Treatment discontinuation; PFS = Prefilled syringe; PSD = Premature subject discontinuation; X = Assessment to be recorded in the source documents and the clinical data base; S = Assessment to be recorded as source documentation only.

Table 6-2 Abbreviated schedule of assessments (ASA) for patients with Treatment Discontinuation (TD)

Visit number	V105-ASA	V108-ASA	V109-ASA	V110-ASA	V111-ASA	V199-ASA	V201-ASA ²
End of Week¹	4	8	12	16	20	24	28
Complete Physical Exam						S	
Brief Physical Exam	S	S	S	S	S		
Weight						X	X
Vital Signs ³	X	X	X	X	X	X	X
Chemistry/Hematology ¹²		X				X	X
Serum Pregnancy						X	
Urine pregnancy	S	S	S	S	S		X
ECG						X	
Clinical Outcomes (eDiary)	eDiary should be maintained						
SF-36 ⁴ (eDiary)	X	X	X	X	X	X	
HIT-6 ⁴ (eDiary)	X	X	X	X	X	X	
C-SSRS	X	X	X	X	X	X	
Concomitant Medications	X	X	X	X	X	X	X
Adverse Events ⁵	X	X	X	X	X	X	X
Serious Adverse Events ⁵	X	X	X	X	X	X	X
Follow Up Phase Completion form							X

1 – All study visit target dates are to be calculated from the Day 1 visit date, and all study procedures for a given visit should be completed in the same day.

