6.5.4.2 Clinical chemistry

Bilirubin (total, direct and indirect), alkaline phosphatase, AST (SGOT), ALT (SGPT), GGT, creatinine and estimated creatinine clearance (GFR) will be measured. Clinical chemistry assessment will be performed at Screening (Visit 0), begin of DBTE (Visit 101), during DBTE two weeks after topiramate titration phase (Visit 108), at the end of DBTE (Visit 199) and at follow up (Visit 201).

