## 2.8.4 Other safety data

### 2.8.4.1 ECG and cardiac imaging data

For the numeric ECG measurements

- ECG Mean Heart Rate
- PR Interval
- QRS Duration
- QT Interval
- QTcF Interval
- RR Interval

summary statistics will be presented for baseline and week 24 separately for each treatment group. Descriptive summary statistics for the change from baseline to the week 24 will be calculated for patients with available ECG data at both time points.

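### By-visit laboratory, ECG and vital-sign tables average values taken after treatment stop into the treatment columns; an on-treatment display should stand beside them

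*SAP*

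**What the plan says.** **Stoppers stay in the study.** Protocol 5.6.2 states: "If discontinuation of study treatment occurs, the patient should NOT be considered withdrawn from the study". It adds that "patients who discontinued treatment from the double-blind treatment epoch will follow the abbreviated visit schedule until the follow up visit (week 28) is reached". Protocol 5.5.4 says the same of early intolerance: "Patients who are not able to tolerate 50 mg have to be discontinued from drug, but should remain in the trial for documentation purposes".

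**What is measured after the stop.** Protocol Table 6-2 schedules vital signs at every abbreviated visit (weeks 4 to 28), chemistry/hematology at weeks 8, 24 and 28, and an ECG at week 24. Protocol 6.5.4.2 places the post-baseline chemistry draws "during DBTE two weeks after topiramate titration phase (Visit 108), at the end of DBTE (Visit 199) and at follow up (Visit 201"), so within the double-blind treatment epoch (DBTE) they fall at weeks 8 and 24.

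**How the SAP places these values.** SAP 2.1.1.2 maps laboratory, vital-sign and ECG values to visits by nearest study-day window, counted from the first dose. SAP 2.1.1.5 assigns them to the DBTE on those windows. SAP 2.8 uses the safety set, which requires only one dose of active medication.

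**How they are summarised.** Laboratory results (SAP 2.8.3) are shown as "absolute value as well as change from baseline by visit, treatment and laboratory test category", and change from baseline requires only a baseline and a post-baseline value. For ECG (SAP 2.8.4.1), "summary statistics will be presented for baseline and week 24 separately for each treatment group". Vital signs (SAP 2.8.4.2) are shown for each study visit. No visible text in these sections sets a last-dose cut-off or a separate summary for the abbreviated visits.

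**The concern.** A week-24 laboratory value from a patient who stopped drug in titration is correctly timed, but it does not describe the patient on drug. It is averaged with the values of patients still being dosed. SAP 2.8 separates the DBTE from the Follow-up Epoch, which does not help here, because the abbreviated visits at weeks 4 to 24 lie inside the DBTE windows.

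The stated purpose (Protocol 1.2) includes comparing safety with topiramate, and the primary hypothesis is that fewer patients stop erenumab because of adverse events. If that holds and other reasons for stopping do not offset it, the topiramate columns carry the larger off-drug share. A between-arm difference in mean change would then reflect stopping rate as well as drug effect, and the planned display gives the reader no way to separate the two.

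**Working it through.** The plan states no figure on this point, so there is nothing to reproduce. The check has three parts.

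**1. Time off drug at the scheduled assessments.** Target days (SAP Table 2.1.1.2-1) are day 57 for week 8 and day 169 for week 24. Injections fall on days 1, 29, 57, 85, 113 and 141 (Protocol 5.5.4). Consider a patient who stops in titration:

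| Last tablet | Last injection | Weeks since tablet / injection at week 8 | Weeks since tablet / injection at week 24 |
|---|---|---|---|
| day 8 | day 1 | (57−8)/7 = 7; (57−1)/7 = 8 | (169−8)/7 = 23; (169−1)/7 = 24 |
| day 43 | day 29 | (57−43)/7 = 2; (57−29)/7 = 4 | (169−43)/7 = 18; (169−29)/7 = 20 |

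The one-week taper, which applies to stoppers on 75 or 100 mg, shortens the tablet gap by one week. Such a patient gives off-drug values at both scheduled DBTE chemistry draws and at the only post-baseline ECG time point that the SAP summarises. Table 6-2 also allows unscheduled chemistry/hematology for adverse events.

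**2. Dilution of the mean.** Let s be the share of an arm that has stopped before the visit, r the share of those stoppers who attend, and E the mean change in patients still on drug. Assume the effect has fully reversed in stoppers.

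- Off-drug share of the values: f = s·r / (1 − s + s·r)
- Reported mean change: (1 − f)·E

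The documents give neither s nor r. Assumed values:

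| s | r = 1 | r = 0.5 |
|---|---|---|
| 5% | 95% of E | 97% of E |
| 10% | 90% | 0.05/0.95 = 0.053, so 95% |
| 20% | 80% | 89% |
| 30% | 70% | 0.15/0.85 = 0.176, so 82% |
| 40% | 60% | 75% |

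If both drugs had the same E, with s = 30% in one arm and 10% in the other, the arm with more stops would look smaller by 0.90 − 0.70 = 20% of E at full attendance, or by 0.947 − 0.824 = about 12% at half attendance. With the roughly 375 patients per arm of SAP 1.1, s = 30% at full attendance means about 0.30 × 375 = 112 off-drug values at week 24.

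**3. Which cut-off would work.** The SAP derives the last syringe date and the last tablet date with taper (2.1.1.1), and uses last syringe date + 27 days in its exposure formula. Applied to everyone, that rule fails at week 24: 141 + 27 = 168, while Visit 199 is targeted at day 169. An erenumab completer seen exactly on schedule would be classed as off drug. Topiramate completers on 75 or 100 mg would stay in, because they taper after Visit 199. Completers on 50 mg have no taper, so they would depend on whether a tablet was taken on the visit day. Completers therefore have to be classed by completion status.

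**The case against.** Summarising all observed values by visit is a legitimate display, and an on-treatment mean has its own flaw: it keeps those who tolerate the drug, and selects them unequally by arm. That stands, and is why the all-values table should remain. The weakness is that it is the only view.

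The size is not anchored. Protocol 5.6.2 lets stoppers be followed by telephone with only medications and adverse events recorded, which adds no off-drug laboratory, ECG or vital-sign value. Fewer patients will have stopped by week 8 than by week 24. An effect that persists after stopping is not diluted at all. Protocol 1.1 and 3.6 report no clinically significant laboratory, vital-sign or ECG changes with erenumab, and the documents give no expected size for a topiramate effect on the measured panel. All of this stands, so the figures are illustrations.

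Signal detection does not rest on these means either. Clinically significant abnormalities are recorded as adverse events (Protocol 7.1), and notable values are flagged and listed individually (SAP 2.8.3). This limits the consequence, although the SAP does not say that the listing shows whether a value was taken on drug. SAP 2.1 leaves output details to table shells that are not part of the documents, so a shell could already narrow the gap.

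A reader might infer that topiramate's effects will be understated by a known amount, or that safety signals will be hidden. The documents support neither. They give no stop rates, attendance or washout times; the primary hypothesis concerns only AE-related stops, whereas the off-drug share depends on all stops; and individual abnormal values remain visible.

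**Conclusion.** The point holds as a gap in the display. As written, the laboratory (weeks 8 and 24), ECG (week 24) and vital-sign (each visit) summaries mix on-drug and off-drug values, and reversible effects are diluted more in the arm with more stops. Under full reversal, an assumed 10% who have stopped leaves 90% to 95% of the on-drug mean change, and 30% leaves 70% to 82%; the lower figure assumes that all stoppers attend and the higher that half do. That topiramate is the more affected arm follows only if the expected imbalance in stopping occurs. The tables are descriptive, and the primary and secondary tests are untouched. This is a low-cost improvement worth making, not a threat to the trial's conclusions.

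**What to change.** In SAP 2.8.3, 2.8.4.1 and 2.8.4.2, keep the all-values by-visit tables, and add on-treatment rows and a separate block labelled as after treatment stop. Define on treatment as follows:

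- **Patients whose double-blind treatment status on the eCRF is not prematurely discontinued (SAP 2.3.1):** all DBTE values, including Visit 199.
- **Patients who stopped early, topiramate arm:** values up to the last IMP tablet dose date, taper included.
- **Patients who stopped early, erenumab arm:** values up to the last IMP syringe dose date + 27 days.

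Flag off-drug values in the listing of clinically notable values.

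The cost is SAP wording, one derived flag and some extra table blocks; no new data are needed. The SAP already excludes doses after discontinuation when it derives the titration dose level (2.1.1), so such a cut-off is feasible. The downside is fewer and more selected patients in the late on-treatment rows, which is why the all-values table stays.
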